7.2.3 Method of Detecting Adverse Events

The method of recording, evaluating, and assessing causality of AEs and SAEs and the procedures for completing and transmitting SAE reports are provided in [Section 9.4](#) (Appendix 4).

Care will be taken not to introduce bias when detecting AEs and/or SAEs. Open-ended and nonleading verbal questioning of the patient is the preferred method to inquire about AE occurrences.

7.2.4 Follow-up of Adverse Events

After the initial AE/SAE report, the Investigator is required to proactively follow each patient at subsequent visits/contacts. All SAEs will be followed until resolution, stabilization, the event is otherwise explained, or the patient is lost to follow-up (as defined in [Section 6.3](#)). Further information on follow-up procedures is given in [Section 9.4](#) (Appendix 4).

7.2.5 Regulatory Reporting Requirements for Serious Adverse Events

- Prompt notification by the Investigator to the Sponsor of a SAE is essential so that legal obligations and ethical responsibilities towards the safety of patients and the safety of a study intervention under clinical investigation are met.
- The Sponsor has a legal responsibility to notify both the local regulatory authority and other regulatory agencies about the safety of a study intervention under clinical investigation. The Sponsor will comply with country-specific regulatory requirements relating to safety reporting to the regulatory authority, IRB/IEC, and Investigators.
- Investigator safety reports must be prepared for suspected unexpected serious adverse reactions (SUSARs) according to local regulatory requirements and Sponsor policy and forwarded to Investigators as necessary.
- An Investigator who receives an investigator safety report describing a SAE or other specific safety information (eg, summary or listing of SAEs) from the Sponsor will review and then file it along with the Investigator's Brochure and will notify the IRB/IEC, if appropriate according to local requirements.

7.2.6 Pregnancy

- The effects of LC on the developing human fetus are unknown, but possible teratogenic effects have been observed in animal and in vitro models. For this reason and because LC as well as TMZ used in this trial are known to be

teratogenic, WOCBP and men must agree to use adequate contraception (hormonal or barrier method of birth control; abstinence) prior to study entry and for the duration of study participation. Should a woman become pregnant or suspect she is pregnant while she or her partner is participating in this study, she should inform her treating physician immediately. Men treated or enrolled on this protocol must also agree to use adequate contraception prior to the study, for the duration of study participation, and 4 months after completion of LC administration.

- Pregnant women are excluded from this study because the curcuminoid moiety of LC has the potential for teratogenic or abortifacient effects at high doses. Specifically, mouse studies using high-dose curcumin have suggested lower fetal birth weights ([Chen et al, 2010](#); [Ganiger et al, 2007](#)), and using pegylated curcumin showed reduced live birth rates in mature females ([Murphy et al, 2012](#)). This same study showed hastened onset of puberty in immature female mice, also raising concerns of potential risk for AEs in nursing infants secondary to treatment of the mother with LC, and breastfeeding should therefore be discontinued if the mother is treated with LC. These potential risks may also apply to other agents used in the study, including but not limited to the co-administration with TMZ which is associated with embryo-fetal toxicity.
- Details of all pregnancies in female patients and in female partners of male patients will be collected from the time of consent until 90 days after the last dose of study drug.
- If a pregnancy is reported, the Investigator should inform the Sponsor within 24 hr of learning of the pregnancy and should follow the procedures outlined in [Section 9.5](#) (Appendix 5).
- Abnormal pregnancy outcomes (eg, spontaneous abortion, fetal death, stillbirth, congenital anomalies, ectopic pregnancy) are considered SAEs.

7.2.7 Deaths

For the first 2 years after the last dose of LC, patients will be followed for survival every 2 months by telephone call, clinic visit, or medical records. After 2 years have elapsed, patients will be followed every 6 months for survival by telephone call, clinic visit, or medical records.

7.3 Efficacy Assessments

The efficacy endpoints of this study are OS and PFS.

Patients with measurable enhancing disease will be assessed by the HGG RANO criteria. Patients should be re-evaluated 1 month after the completion of concurrent CRT as well as every 2 cycles (approximately every 8 weeks) with a contrast-enhanced cranial MRI scan. Evidence of PD will be determined as outlined in the RANO criteria below.

7.3.1 Definition of Evaluable for Efficacy

Enrolled patients are newly diagnosed and there are no restrictions on amount of measurable disease from biopsy, subtotal, or gross total resection. These patients will have their disease evaluated according to the definitions stated below. (Note: Patients who exhibit objective disease progression prior to the end of Cycle 1 will also be considered evaluable.)

7.3.2 Disease Parameters

Measurable Disease: Bidimensionally, contrast-enhancing, measurable lesions with clearly defined margins by MRI scan, with a minimal size of 1 cm by 1 cm, and visible on 2 axial slices which are at least 5 mm apart with 0-mm skip. Measurement of tumor around a cyst or surgical cavity, if necessary, requires a minimum thickness of 3 mm. If there are > 2 lesions (multifocal) at baseline, the Investigator must choose the largest 2 to be followed before a patient is entered on study. The remaining lesions will be considered nonmeasurable for the purpose of objective response determination. Unless progression is observed, objective response can only be determined when all measurable and nonmeasurable lesions are assessed.

Target Lesions: In multifocal disease, all measurable lesions within the brain should be identified as **target lesions** and recorded and measured at baseline. A sum of the diameters (longest for non-nodal lesions, short axis for nodal lesions) for all target lesions will be calculated and reported as the baseline sum diameters. The baseline sum diameters will be used as reference to further characterize any objective tumor regression in the measurable dimension of the disease.

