7.3.4 Use of Criteria from Response Assessment in Neuro-Oncology for Assessment of Progression

Progressive disease is defined by *any* of the following:

- a) $\geq 25\%$ increase in sum of the products of perpendicular diameters of enhancing lesions compared to the smallest tumor measurement obtained either at baseline

- (if no decrease) or best response, on stable or increasing doses of corticosteroids. (Stable doses of corticosteroids include patients not on corticosteroids.)
- b) Significant increase in T2-fluid-attenuated inversion recovery (FLAIR) nonenhancing lesion on stable or increasing doses of corticosteroids compared to baseline scan or best response following initiation of therapy, not due to comorbid events (RT, demyelination, ischemic injury, infection, seizures, postoperative changes, or other treatment effects)
 - c) Any new lesion
 - d) Clear clinical deterioration not attributable to other causes apart from the tumor (eg, seizures, medication adverse effects, complications of therapy, cerebrovascular events, infection, etc) or changes in corticosteroid dose. A diagnosis of clinical progression or deterioration may be made at the discretion of the treating physician.
 - e) Failure to return for evaluation due to death or deteriorating condition
 - f) Clear progression of nonmeasurable disease

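### Protocol 7.3.2 specifies a baseline sum of diameters, but the progression criterion in 7.3.4(a) needs a sum of products of perpendicular diameters, and the set of lesions to be summed is unclear

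*Protocol*

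**What the plan says.** **Baseline measurement (Protocol 7.3.2).** Measurable disease is defined in two dimensions, at least 1 cm by 1 cm. The burden to be calculated and reported at baseline has one dimension per lesion: "A sum of the diameters (longest for non-nodal lesions, short axis for nodal lesions) for all target lesions will be calculated". Its stated use is regression: "The baseline sum diameters will be used as reference to further characterize any objective tumor regression".

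**Lesion set (also 7.3.2).** With more than 2 lesions at baseline, "the Investigator must choose the largest 2 to be followed", and "The remaining lesions will be considered nonmeasurable for the purpose of objective response determination". The paragraph on target lesions then says: "In multifocal disease, all measurable lesions within the brain should be identified as" target lesions.

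**Progression (7.3.4).** Criterion (a) is a rise of at least 25% in the "sum of the products of perpendicular diameters of enhancing lesions compared to the smallest tumor measurement", taken at baseline if there has been no decrease and otherwise at best response. Criterion (f) is clear progression of nonmeasurable disease.

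**Use.** Section 7.3 names overall survival and PFS as the efficacy endpoints. Section 8.4.7 estimates PFS by Kaplan-Meier on the RANO criteria. Section 8.1 states that no hypotheses are tested.

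**The concern.** The measurement section and the progression section describe different quantities. The only baseline sum that 7.3.2 requires is tied to regression, and the trial has no response endpoint. The sum that criterion (a) needs is nowhere stated to be calculated or recorded, at baseline or at later scans.

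The two sections also meet through best response. Criterion (a) measures growth from the smallest value after any decrease, so the scale used to recognize a decrease helps to fix the starting point for progression. If regression is tracked on diameters and progression on products, the reference scan need not be the same.

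The nodal rule has no use in a paragraph confined to lesions within the brain.

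The lesion set matters separately. A third lesion of measurable size is either part of the sum in (a) or nonmeasurable disease judged under (f), depending on which sentence is followed. At stake is the consistency of PFS dates among locally read scans (4.1.5).

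**Working it through.** The plan states no figure to reproduce here. The check asks whether one sum can stand in for the other, and whether the choice of lesion set can change a call. The 25% threshold comes from 7.3.4(a). All lesion sizes are assumed, for illustration only; each is at least 1 cm by 1 cm.

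**1. Can a sum of diameters be converted to a sum of products?** A sum of longest diameters of 40 mm fits all of these:

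| Lesions (mm) | Sum of longest diameters | Sum of products |
|---|---|---|
| 40x10 | 40 mm | 400 mm² |
| 30x20 and 10x10 | 30 + 10 = 40 mm | 600 + 100 = 700 mm² |
| 20x20 and 20x20 | 20 + 20 = 40 mm | 400 + 400 = 800 mm² |
| 40x40 | 40 mm | 1600 mm² |

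One diameter sum is compatible with a fourfold range of products, so no conversion exists.

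**2. Can the two sums disagree on change?** A lesion grows from 30x20 to 30x25 mm.
- Product: 750/600 − 1 = +25.0%, which meets criterion (a).
- Longest diameter: 30/30 − 1 = 0%.

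**3. Can the lesion set change the call?** Lesions of 40x30, 20x20 and 20x18 mm; the first grows to 46x35 mm and the others do not change.
- Products at baseline: 1200, 400 and 360 mm². The first becomes 1610 mm².
- Largest 2: (1610 + 400)/(1200 + 400) − 1 = 2010/1600 − 1 = +25.6%, progression under (a).
- All 3: (1610 + 400 + 360)/(1200 + 400 + 360) − 1 = 2370/1960 − 1 = +20.9%, no progression under (a).
- Sum of longest diameters, all 3: 86/80 − 1 = +7.5%.

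The same scan is progression under one sentence of 7.3.2 and not under the other.

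**4. Relation of the scales under equal growth in both axes.** The product ratio is the square of the diameter ratio. A 25% rise in product is √1.25 − 1 = 11.8% in diameter. A 25% rise in diameter is 1.25² − 1 = 56.25% in product.

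**The case against.** The best defense is that 7.3.4(a) states its own metric. A 25% increase in a sum of products is naturally read against an earlier value of that same sum, and 7.3 sends the reader to those criteria for progression. The diameter sum has a different stated purpose, regression. This stands: the protocol does not designate a wrong reference for progression; it leaves the right one unstated.

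A reader might infer from step 4 that sites will apply 25% to diameters, need a 56% rise in product, and call progression late. The protocol does not support that, because no section applies 25% to a sum of diameters.

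A reader might also infer that the baseline value will be lost. That does not follow either. Measurable disease is bidimensional, 7.3.2 and 7.3.3 ask for lesions to be measured and the measurements recorded, and both diameters can be read from the MRIs. The case report form is not at hand, so nothing can be said about its fields.

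On the lesion set, the sentence that treats lesions beyond the largest 2 as nonmeasurable lets one read all measurable lesions in the next paragraph as those 2. That reading is possible but not stated, and the nonmeasurable label is given only for response determination, so the ambiguity remains.

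The statistical analysis plan, which is not shown, might define the analysis variable. But these are measurement instructions to sites, and 8.4 requires that plan to be final only before database lock, after most scans have been read.

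**Conclusion.** The concern holds as a measurement rule that does not fit the criterion PFS uses. Section 7.3.2 requires a sum that no endpoint uses, leaves the sum needed by 7.3.4(a) implied, and does not settle which lesions enter it. The illustrations show that the sums are not interchangeable (+25% against 0%) and that the lesion set alone can move a call across the threshold (+25.6% against +20.9%). They rest on assumed lesion sizes and show what can happen, not how often.

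The reach is narrow. Criterion (a) is affected and, through the lesion set, criterion (f). Criteria (b) to (e) and death do not use the sum. The lesion-set question arises only with more than 2 lesions, and some patients may have no measurable enhancing lesion after resection (7.3.1 sets no minimum). PFS is a secondary, descriptive endpoint in up to 24 escalation and 6 expansion patients (8.2), and dose decisions rest on dose-limiting toxicity. It would go too far to say that PFS dates will generally depend on which section a site followed. The correction should still be made, because it is specific and nearly free.

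**What to change.** In 7.3.2, delete the sum-of-diameters sentences, including the nodal rule. State instead that the sum of products of perpendicular diameters of the target lesions is calculated and recorded at baseline and at each MRI, and that the smallest of these values (baseline if there has been no decrease, otherwise best response) is the reference for 7.3.4(a).

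Reconcile the largest-2 and all-measurable statements into one defined set of target lesions, and say that measurable-size lesions outside that set, if any, are handled under 7.3.4(f).

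The cost is a protocol wording change and, if the case report form does not already hold it, a field for the sum of products. No new scans or visits are needed. For patients already enrolled, the sums can be derived from the existing MRIs.

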7.3.3 Methods for Evaluation of Measurable Disease

All measurements should be taken and recorded in metric notation using a ruler or calipers. All baseline evaluations should be performed on post-resection imaging.

Magnetic resonance imaging will be used to evaluate lesions. The same technique should be used to characterize each identified and reported lesion at baseline and during follow-up.

The technical specifications of the scanning sequences used should be optimized if performed outside of the Hopkins system. A glioma-specific radiological protocol has been standardized for scanners within the Hopkins system. Lesions should be measured/assessed on the same pulse sequence as was used at baseline. Ideally, the same type of scanner should be used and the image acquisition protocol should be followed as closely as possible to prior scans.

7.3.4 Use of Criteria from Response Assessment in Neuro-Oncology for Assessment of Progression

Progressive disease is defined by *any* of the following:

- a) $\geq 25\%$ increase in sum of the products of perpendicular diameters of enhancing lesions compared to the smallest tumor measurement obtained either at baseline

- (if no decrease) or best response, on stable or increasing doses of corticosteroids. (Stable doses of corticosteroids include patients not on corticosteroids.)
- b) Significant increase in T2-fluid-attenuated inversion recovery (FLAIR) nonenhancing lesion on stable or increasing doses of corticosteroids compared to baseline scan or best response following initiation of therapy, not due to comorbid events (RT, demyelination, ischemic injury, infection, seizures, postoperative changes, or other treatment effects)
 - c) Any new lesion
 - d) Clear clinical deterioration not attributable to other causes apart from the tumor (eg, seizures, medication adverse effects, complications of therapy, cerebrovascular events, infection, etc) or changes in corticosteroid dose. A diagnosis of clinical progression or deterioration may be made at the discretion of the treating physician.
 - e) Failure to return for evaluation due to death or deteriorating condition
 - f) Clear progression of nonmeasurable disease

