4.1.5 Evaluation of Toxicity and Response

- For dose escalation purposes, the DLT evaluation period is defined as the first 10 weeks of treatment (ie, 6 weeks of CRT plus LC followed by a 4-week post-CRT period).
 - Patients are available for DLT evaluation if they have either:
 - Received at least 80% of the planned doses of LC (8 of the planned 10 doses), at least 80% of the planned RT, and at least 60% of the planned TMZ
- OR

- Experienced a DLT in the first 10 weeks of treatment
- Dose finding will be performed using a TITE-BOIN schema as outlined in [Section 8.4.9](#). The window for DLT evaluation and decisions regarding dose advancement or de-escalation will be based on events occurring during the first 10 weeks of the study, though further data regarding safety and tolerability will be collected on every patient continuing infusions through the adjuvant TMZ treatment period.
- Standard contrast magnetic resonance imaging (MRI) will be used for assessment of progression, following the Response Assessment in Neuro-Oncology (RANO) criteria for PD. Patients will have a baseline MRI study followed by CRT, an MRI at the beginning of the adjuvant TMZ phase (4 weeks after completion of CRT) and another MRI every 2 cycles thereafter as per standard of care. More frequent imaging may be clinically necessary per the discretion of the treating physicians.
- MRI scans will be assessed locally by board-certified neuroradiologists who will independently assess tumor size and radiographic changes.
- For the first 2 years after the last dose of LC, patients will be followed for survival and progression every 2 months by telephone call, clinic visit, or medical records. After 2 years have elapsed, patients will be followed every 6 months for survival and progression by telephone call, clinic visit, or medical records.
- For the purposes of analyses, the duration of each arm will last through the 6 weeks of CRT, the 4-week post-CRT period, and the adjuvant cycles received by the patient.

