Less Likely:

- Nausea
- Vomiting
- Permanent mental slowing
- Permanent hearing loss
- Cataracts
- Behavioral change
- Temporary worsening of existing neurological deficits, such as decreased vision, drowsiness
- Changes in the level of some hormones related to changes to the pituitary gland
- Dry mouth or altered taste

Uncommon but Serious:

- Severe local damage to normal brain tissue, a condition called necrosis (tissue deterioration). Radiation necrosis can mimic recurrent brain tumor and may require surgery for diagnosis and treatment.
- Injury to brain causing permanent neurologic deficits or disability
- Injury to brain causing severe cognitive slowing
- Injury to the eyes with the possibility of blindness

Rare

- Development of other tumors (either benign or malignant)

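### The progression rule excludes radiation and treatment effects for nonenhancing and clinical change but not for enhancing disease or new lesions, so radiation-related enhancement on the first post-CRT MRI can count as a PFS event

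*Protocol*

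**What the plan says.** Section 7.3 sends the assessment of progression to the criteria printed in Section 7.3.4, where meeting any one of items (a) to (f) is enough.

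- Item (a) is a rise of at least 25%: "increase in sum of the products of perpendicular diameters of enhancing lesions compared to the smallest tumor measurement obtained either at baseline". Its qualifier reads "if no decrease) or best response, on stable or increasing doses of corticosteroids".
- Item (b), for T2/FLAIR nonenhancing disease, carries the same steroid condition and must also be "not due to comorbid events (RT, demyelination, ischemic injury, infection, seizures, postoperative changes, or other treatment effects".
- Item (c) reads in full "Any new lesion".
- Item (d) is "Clear clinical deterioration not attributable to other causes apart from the tumor (eg, seizures, medication adverse effects, complications of therapy" and further examples.
- Item (f), on nonmeasurable disease, has no exclusion by cause.

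On the reference scan, Section 7.3.3 says "All baseline evaluations should be performed on post-resection imaging". The MRI footnote to the Schedule of Activities places that scan before the first study drug dose, and Section 4.1 starts liposomal curcumin (LC) with CRT. On follow-up, Section 4.1.5 schedules "an MRI at the beginning of the adjuvant TMZ phase (4 weeks after completion of CRT") and then an MRI every two cycles.

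Section 5.5.4.1, under its uncommon-but-serious heading, states: "Radiation necrosis can mimic recurrent brain tumor and may require surgery for diagnosis and treatment".

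PFS is a secondary endpoint by dose level (Section 3), estimated by Kaplan-Meier on these criteria (Section 8.4.7). Disease progression is also a reason to end treatment (Section 4.1.2).

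**The concern.** The authors saw that radiation and other treatment can produce change that is not tumor growth, and they excluded it for nonenhancing and clinical progression. They did not carry the exclusion to enhancing disease or new lesions. Section 7.3.4 also has no confirmatory scan, no time window after radiation, no in-field rule and no reset of the baseline.

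The scan most exposed to this is the first one: it follows the full radiation course and is compared with an unirradiated baseline. At stake is the meaning of early PFS events. An unknown share could be imaging change caused by treatment, and PFS is one of only two efficacy endpoints in a study meant to inform a later efficacy trial.

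**Working it through.** **1. Items side by side (Section 7.3.4).**
- (a) enhancing rise: steroid dose only.
- (b) nonenhancing change: steroid dose, plus radiation and other treatment effects excluded.
- (c) new lesion: no qualifier.
- (d) clinical deterioration: other causes excluded, including therapy complications.
- (f) nonmeasurable disease: must be clear, with no exclusion by cause.

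So two items exclude treatment effects, and the two imaging items on enhancing or new disease do not.

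**2. Timing.** Section 9.2.2 gives 30 × 2 Gy = 60 Gy. Fractions are Monday to Friday from D1, with at least two in the first week (Section 9.2.7), so D1 is Monday to Thursday. The 30th fraction then falls on D40 (Monday start) or D42. Adjuvant Week 1 is D71.
- 71 − 40 = 31 days and 71 − 42 = 29 days, or 4.4 and 4.1 weeks. This reproduces the stated 4 weeks.
- With the ±3-day visit window: 26 to 34 days.
- With the 33 fractions that Section 4.1 also allows, the last falls on D45 to D47, a gap of 26 to 24 days (3.7 to 3.4 weeks).

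**3. How much change meets item (a).** A 25% rise in the product, shared equally by both diameters, is √1.25 = 1.118 per diameter. A lesion at the 10 × 10 mm minimum of Section 7.3.2 qualifies at about 11.2 × 11.2 mm, whatever the cause.

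**4. Size, under an assumption.** The documents give no rate. Let q be the share of patients who meet (a) or (c) at this scan only because of radiation-related change, with q assumed to be 10% to 30%. If all n patients are enrolled and still progression-free at the scan, expected false events are n × q:
- n = 30 (maximum treated, Section 1.1): 30 × 0.10 = 3 to 30 × 0.30 = 9.
- n = 12 (escalation cap at one dose, Section 4.1.2): 1.2 to 3.6.
- n = 6 (expansion, Section 8.6): 0.6 to 1.8. The chance of at least one is 1 − 0.90^6 = 0.47 to 1 − 0.70^6 = 0.88.

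Fewer patients reaching the scan progression-free lowers all of these.

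**5. Effect on median PFS, illustration only.** Assume exponential PFS with true median m, and that a share q of those still progression-free at Week 10 is wrongly called. After Week 10 the observed curve is S(t)(1 − q), so the observed median is m × [ln 2 + ln(1 − q)] / ln 2.
- m = 8 months, q = 10%: 8 × (0.693 − 0.105)/0.693 = 6.8 months.
- m = 8 months, q = 30%: 8 × (0.693 − 0.357)/0.693 = 3.9 months.
- For m from 6 to 10 months: 5.1 to 8.5 months at q = 10%, and 2.9 to 4.9 months at q = 30%.

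**6. Is a confirming scan available?** A patient who continues has an MRI before Adjuvant Cycle 3. Under Section 4.1.2 a patient called as progressed stops treatment. The End of Treatment MRI need not be repeated if one was done in the prior 14 days, and Section 7.3.6 then follows progression by phone, clinic visit or records, with no scheduled MRI.

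**The case against.** The strongest reply is that PFS is secondary and that Section 8.1 makes all analyses descriptive, so no error rate or sample size depends on it. Dose groups are small and mix tumor grades and molecular types, so PFS could not be compared between doses with confidence anyway. Local neuroradiologists read the scans, extra imaging is allowed at the physicians' discretion, and an SAP could add a PFS sensitivity analysis. All of this stands and limits the weight of the point. It does not remove it: reader judgement is not a rule, the definition of progression is fixed in this protocol, and after an early stop the scans that an SAP would need may not exist.

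A reader might infer more than the documents support:
- **That only item (b) guards against treatment effects.** Item (d) does too.
- **That mimicry is frequent at 4 weeks.** Section 5.5.4.1 lists necrosis as uncommon and gives no timing.
- **That edema, listed as a likely radiation effect, shows the same problem.** It is mainly a T2/FLAIR change, and item (b) already excludes radiation-related change there.
- **That the artefact rises with LC dose because curcumin is described as radiosensitizing.** Section 2 rests this on preclinical and cell-line work, so a dose trend is conjecture.

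**Conclusion.** The gap is real and follows from the protocol's own text: items (a) and (c) lack the exclusion found in (b) and (d), no confirmation is required, and the first post-radiation scan is judged against a pre-radiation baseline. Followed as written, the rule counts radiation-related enhancement that meets (a) or (c) as a PFS event.

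The size cannot be derived from the documents. Three to nine events in 30 patients is a ceiling, not an estimate. It rests on the assumed 10-30%, on full enrolment, and on every patient being progression-free at that scan. Enhancement below the 25% threshold with no new lesion is not an event under (a) or (c).

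A reader might also infer that dose selection is compromised. It is not: DLT and feasibility are measured over the first 10 weeks and do not use this definition. A patient wrongly stopped at Week 10 would forgo 24 of 34 planned weekly infusions (71%), which costs later safety data but not the primary endpoint.

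**What to change.** For the PFS endpoint, amend Section 7.3.4 as follows:
- Extend the item (b) exclusion for radiation and other treatment effects to items (a) and (c), and check item (f) for the same gap.
- Where a later MRI is available, count an enhancing increase or new in-field lesion on the first post-CRT MRI as progression only if the later MRI confirms it, with the event dated back to the first scan.
- State how patients with no later MRI, or who start other therapy before one, are counted.
- Report PFS both ways, under the present rule and under the amended one, as a sensitivity analysis.

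The exclusion itself is a wording change. Confirmation is not free: it will be missing for patients who stop at Week 10, because no MRI is scheduled after treatment ends. The exclusion also brings some local judgement of cause into an open-label study, which is why both versions should be shown.

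Sections 4.1.2 (stopping for progression), 4.1.5 (scan timing), 5.5.4.1 (radiation effects), 7.3.4 (progression) and 7.3.6 (follow-up) must be reconciled. No treatment rule is proposed here.
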